6 SCHEDULE OF ASSESSMENTS AND PROCEDURES

Individual trial procedures are detailed in Tables 5-7. It may be necessary to perform these procedures at unscheduled time points if deemed clinically necessary by the Treating and Examining Neurologists.

Additional evaluations/testing may be deemed necessary by the Treating Neurologist and/or the Sponsor for reasons related to subject safety.

Table 5: Schedule of Assessments and Procedures: Screening through Week 20

	Screening	Baseline		Treatment Period							Unscheduled Relapse Visit ¹⁴	
	Week		W1	W1	W2	W3	W4	W8 ⁴	W12 ⁴	W16 ⁴	W20 ⁴	
	Day ⁴	D (-28 to 0)	D1	D2	D8	D15	D28	D56 ⁴	D84 ⁴	D112 ⁴	D140 ⁴	
Subject consent	X											X ¹⁰
Medical history	X											
Serum pregnancy test ¹	X ¹¹											X
Urine pregnancy test ^{1,5}					X	X	X	X	X	X	X	
EDSS, MSFC, and neurological examination ^{4,13}	X	X ²²							X			X ¹⁸
Physical examination ⁸ & vital signs (heart rate, blood pressure, temperature and body weight) ^{4,13}	X	X	X	X	X	X	X	X	X	X	X	X
MSQoL ⁵⁴ (inclusive of SF36), SDMT, and FIS assessment ¹³		X										
MRI ^{4,13}	X								X			
Subject diary and teriflunomide or oral placebo dispensation		X							X			
12 lead ECG ⁹	X	X			X							
Blood collection for CBC, pancreatic enzymes and serum chemistry ^{3,4,20}	X	X	X	X	X	X	X	X	X	X	X	X
Urinalysis ¹³	X	X	X	X	X	X	X	X	X	X	X	X
Blood collection for B lymphocyte cell counts (% CD19+ B cells) ^{3,4}	X	X	X	X	X	X	X	X	X	X	X	X
Fibrinogen ^{3,4}		X			X							X
Teriflunomide drug concentration test		X ^{3,17}										
Subject diary review and teriflunomide/oral placebo accountability		X	X	X	X	X	X	X	X	X	X	X
Serology: HIV, HCV, HBV, varicella ²	X											
Anti-Drug Abs (ADA) ^{3,7}		X			X							
PT/INR ⁵		X										
Quantitative immunoglobulin ^{3,4,13}		X			X							X
Adverse events (CTCAE v4.03)		X	X	X	X	X	X	X	X	X	X	X
Concomitant medication	X	X	X	X	X	X	X	X	X	X	X	X
Ublituximab/placebo infusion ²⁴		X			X							
Initiate teriflunomide/oral placebo administration ¹⁶		X										

Table 6: Schedule of Assessments and Procedures: Weeks 24 through 84

Week	Treatment Period						Unscheduled Relapse Visit ¹⁴
	W24 ⁴	W36 ⁴	W48 ⁴	W60 ⁴	W72 ⁴	W84 ⁴	
	Day ⁴	D168 ⁴	D252 ⁴	D336 ⁴	D420 ⁴	D504 ⁴	
Subject consent							X ¹⁰
Urine pregnancy test ^{1,5,21}	X	X	X	X	X	X	
Serum pregnancy test ¹							X
EDSS, MSFC and neurological examination ^{4,13}	X	X	X	X	X	X	X ¹⁸
Physical examination ⁸ & vital signs (heart rate, blood pressure, temperature and body weight) ^{4,13}	X	X	X	X	X	X	X

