⁴ Weeks 8 and beyond, collections/assessments may occur ± 5 days from specified time points, except for MRI scans, which can occur ± 7 days on Weeks 12 and 96 and must be performed pre-infusion on infusion days (- 7 days) on Weeks 24 and 48. MRI scan at Early Withdrawal from Treatment Visit should be performed within 4 weeks after withdrawing from the study.

⁵ Prior to each infusion except PT/INR which is completed at baseline. Urine Pregnancy Test on non-infusion days subjects will test upon arrival at the site

⁶ Prior to infusion and 30 minutes +/- 15 minutes post-infusion on infusion days. For non-infusion days, one PK sample should be obtained

⁷ Anti-Drug Antibodies are antibodies developed against ublituximab

⁸ Physical examination will occur on all visits except Week 1 Day 2 and Week 2 Day 8

⁹ Within 2 hours pre-infusion and 60 minutes +/- 15 minutes post-infusion on any infusion day

¹⁰ Re-consent following a suspected relapse is required if the relapse is confirmed by IRAP or by the Treating Neurologist (Treating Neurologist medically confirmed relapse), whichever comes first. Re-consent must occur within 6 weeks after first reporting of relapse. Re-consent may occur at the next schedule office visit but may require an unscheduled visit if the relapse occurs between Weeks 24 and 96 (where the frequency of scheduled visits is every 12 weeks).

¹¹ Serum pregnancy test must be completed within 5 days prior to Week 1 Day 1

¹² Obtain blood sample for teriflunomide drug concentration test prior to first dose of accelerated teriflunomide elimination procedure

¹³ Prior to each infusion

¹⁴ The Unscheduled Relapse Visit will be conducted if a possible relapse is reported by the subject. The visit is to be planned as soon as possible, within 7 days from subject notification of the relapse to the site. Infusion visit is delayed until relapse is back to baseline, or Treating Neurologist/PI does not expect any improvements.

¹⁶ Teriflunomide/oral placebo administration shall be taken in the morning until the last day of Week 95. Alternative dosing times are allowed if necessary.

¹⁷ Sample for teriflunomide concentration to be collected before the first oral dose of teriflunomide/oral placebo

¹⁸ For Unscheduled Relapse Visit, EDSS assessment (by Examining Neurologist) and neurological examination (by Treating Neurologist) will be performed independently

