6.1 OVERVIEW

All subjects should visit the study center on the days specified within this protocol. The complete schedule of assessments is shown in Section 6 (Tables 5, 6, and 7) and Appendix F. The screening physical examination with vital signs, medical history, evaluation of concomitant medications, EDSS (fatigue will not contribute to the EDSS score), complete blood count/full blood count (3 part differential accepted), serum chemistry, and a baseline ECG should be done within 28 days prior to initiation of treatment. For women of child bearing potential, a serum pregnancy test should be completed within 5 days prior to Week 1 Day 1. MRI scans should be performed ≤ 28 days prior to initiation of treatment.

Week 1/Day 1 EDSS must be assessed within 1 day prior to randomization (i.e., on the day before randomization or on the day of randomization but before randomization occurs) and must be documented.

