6.3.7 SAFETY DATA

Subject safety will be evaluated throughout the study during the following assessments:

- Adverse events
- Physical examination: cardiovascular system, chest and lungs, thyroid, abdomen, nervous system, skin and mucosae, and musculoskeletal system, eyes, ears, nose, mouth, throat, spine, lymph nodes, extremities, genitourinary, weight
- Hematology and differential panel: hemoglobin, hematocrit, red blood cell count, mean corpuscular hemoglobin, white blood cell count, neutrophils, lymphocytes, monocytes, eosinophils, basophils, and platelets
- Fibrinogen
- Pregnancy testing (serum or urine levels of β -human chorionic gonadotrophin (HCG)) in women of childbearing potential). In addition, pregnancy test should be conducted in case of an unexpected delay of menorrhoea
- ECG (within 2 hours pre-infusion and 60 minutes +/- 15 minutes post-infusion on days of infusion; for non-infusion days one ECG assessment should be performed)
- Blood chemistry panel: Albumin, Alkaline Phosphatase, BUN, Calcium, Chloride, Creatinine, Glucose, LDH, Magnesium, Phosphate, Potassium, SGOT (AST), SGOT (ALT), Sodium, Total Bilirubin, Total Protein, Uric Acid, and direct/ indirect bilirubin
- Liver function panel: SGOT/AST, SGPT/ALT, serum gamma-glutamyl transferase (SGGT), total bilirubin, direct/indirect bilirubin.
- Pancreatic enzyme panel: serum amylase and lipase

- Urinalysis panel for routine safety: pH, ketones, protein, glucose, blood, urobilinogen, bilirubin, microscopic sediment, specific gravity and leucocyte esterase.
- Vital signs: (within 2 hours pre-infusion and 60 minutes +/- 15 minutes post-infusion on days of infusion) systolic and diastolic blood pressure, heart rate, body temperature, and weight

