Alkaline phosphatase	LDH	Sodium																							
Bicarbonate	Magnesium	Total bilirubin																							
BUN	Phosphorus	Total Protein																							
Calcium	Potassium	Uric acid																							
Chloride	SGGT	Indirect/direct bilirubin																							
Creatinine	SGOT [AST]																								
Documents / Forms:	 Informed Consent Form  Signed Eligibility Screening Worksheet  MRI data transfer to Central MRI Reading Center																								
Drug Preparation / Dispensation:	None																								
Timing and Sequence Considerations:	Once signed consent is obtained, procedures can be scheduled for the day at investigator and subject convenience. We recommend that labs be performed prior to MRI with Gadolinium contrast agent.																								

Visit:	Week 1 Day 1																								
Time Required:	Full day; Allow 8 hours																								
Treatment:	 Ublituximab 150 mg or placebo infusion in 250 mL volume; 4 hour infusion time 
 • Pre-medicate 30-60 minutes prior to each dose of ublituximab or IV placebo with an antihistamine (diphenhydramine 50 mg or equivalent), and corticosteroid (dexamethasone 10-20 mg or equivalent). Oral acetaminophen, 650 mg (or equivalent; only used for intervention) should be restricted to subject who experience fever or pyrexia after Week 1 dose, or as clinically warranted and additional medication (which needs to be documented) may be used at discretion of the physician if adverse reactions occur.  Teriflunomide (14 mg) or oral placebo until last day of Week 95																								
Tests:	 12 Lead ECG; pre- and post-infusion																								
Clinical Assessments:	 Adverse Event  Concomitant medications  Physical examination/vital signs  EDSS, MSFC, MSQOL54, SDMT, FIS and neurological examination																								

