Labs: (see Laboratory Manual for full details, instructions, and shipping information)	 Hematologic profile; CBC/FBC with differential and platelet count  Serum chemistry panel; 
  
 Serum Chemistry	
   
 Albumin	Glucose	SGPT [ALT]	
 
 Alkaline phosphatase	LDH	Sodium	
 
 Bicarbonate	Magnesium	Total bilirubin	
 
 BUN	Phosphorus	Total Protein	
 
 Calcium	Potassium	Uric acid	
 
 Chloride	SGGT	Indirect/direct bilirubin	
 
 Creatinine	SGOT [AST]		
  
  Pancreatic Enzyme  Absolute B cell lymphocyte count and % B cell  Urinalysis  Fibrinogen  Quantitative Immunoglobulin; Total Ig, IgG, IgM, IgA  PT/INR  Pharmacokinetics (for all subjects); Prior to first infusion and at 30 minutes +/- 15 minutes after end of infusion on infusion day  Anti-Drug Antibodies; Drawn prior to infusion  Teriflunomide Drug Concentration Test; Collected before first oral dose of teriflunomide or oral placebo	Serum Chemistry			Albumin	Glucose	SGPT [ALT]	Alkaline phosphatase	LDH	Sodium	Bicarbonate	Magnesium	Total bilirubin	BUN	Phosphorus	Total Protein	Calcium	Potassium	Uric acid	Chloride	SGGT	Indirect/direct bilirubin	Creatinine	SGOT [AST]	
Serum Chemistry																									
Albumin	Glucose	SGPT [ALT]																							
Alkaline phosphatase	LDH	Sodium																							
Bicarbonate	Magnesium	Total bilirubin																							
BUN	Phosphorus	Total Protein																							
Calcium	Potassium	Uric acid																							
Chloride	SGGT	Indirect/direct bilirubin																							
Creatinine	SGOT [AST]																								
Documents / Forms:	 Subject Randomization  eCRF documentation  Infusion Log																								

- AE and SAE Reporting (If applicable)
- Sample shipping
- Teriflunomide or oral placebo dispensation
- Dispensing of Subject Diary

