 - All labs and ADA, drawn prior to start of pre-treatment and infusion
 - PK
 - Physical examination, EDSS and clinical assessments pre-infusion
 - 12 lead ECG
 - Vital signs
- During infusion
- Infusion log
- Post Infusion
- Additional PK at 30 minutes +/- 15 minutes after end of infusion
 - 12 lead ECG

Visit: | Week 84 Day 588

Time Required:	Approximately 1 hour																								
Treatment:	 Teriflunomide (14 mg) or oral placebo until last day of Week 95																								
Tests:	 Urine Pregnancy Test; Must have confirmed negative result																								
Clinical Assessments:	 Adverse Event  Concomitant medications  Physical examination/vital signs  EDSS, MSFC and neurological examination																								
Labs: (see Laboratory Manual for full details, instructions, and shipping information)	 Hematologic profile; CBC/FBC with differential and platelet count  Serum chemistry panel; 
  
 Serum Chemistry	
   
 Albumin	Glucose	SGPT [ALT]	
 
 Alkaline phosphatase	LDH	Sodium	
 
 Bicarbonate	Magnesium	Total bilirubin	
 
 BUN	Phosphorus	Total Protein	
 
 Calcium	Potassium	Uric acid	
 
 Chloride	SGGT	Indirect/direct bilirubin	
 
 Creatinine	SGOT [AST]		
  
  Pancreatic Enzyme  Absolute B cell lymphocyte count and % B cell  Urinalysis	Serum Chemistry			Albumin	Glucose	SGPT [ALT]	Alkaline phosphatase	LDH	Sodium	Bicarbonate	Magnesium	Total bilirubin	BUN	Phosphorus	Total Protein	Calcium	Potassium	Uric acid	Chloride	SGGT	Indirect/direct bilirubin	Creatinine	SGOT [AST]	
Serum Chemistry																									
Albumin	Glucose	SGPT [ALT]																							
Alkaline phosphatase	LDH	Sodium																							
Bicarbonate	Magnesium	Total bilirubin																							
BUN	Phosphorus	Total Protein																							
Calcium	Potassium	Uric acid																							

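### The post-infusion vital-signs reading required by Protocol 6.3.7 is missing from the schedule tables and from all five infusion-visit lists in Appendix F

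*Protocol*

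**What the plan says.** Protocol 6.3.7 (Safety Data) states the rule: "Vital signs: (within 2 hours pre-infusion and 60 minutes +/- 15 minutes post-infusion on days of infusion". The ECG entry in the same section has the same window.

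Protocol 6.1 tells sites where to find the full list of what to do and when: "The complete schedule of assessments is shown in Section 6 (Tables 5, 6, and 7) and Appendix F".

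In Tables 5 and 6, "vital signs (heart rate, blood pressure, temperature and body weight" shares a row with the physical examination. The row carries footnotes 4 and 13, and footnote 13 reads "Prior to each infusion". The ECG row carries footnote 9: "Within 2 hours pre-infusion and 60 minutes +/- 15 minutes post-infusion on any infusion day".

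In Appendix F, the checklist for each infusion visit shows the ECG as "12 Lead ECG; pre- and post-infusion" and lists physical examination and vital signs with no timing. The sequence lists at the end of each infusion visit place vital signs before the infusion only. From Week 3 Day 15 onward, the list of tasks after the infusion holds a PK sample (for example "Additional PK at 30 minutes +/- 15 minutes after end of infusion", Week 72) and the ECG, and nothing else.

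**The concern.** The protocol gives one rule in its safety section and a narrower one in the schedule and visit lists. A coordinator following the lists takes vital signs before the infusion, draws the PK sample and records the ECG afterwards, and has no prompt for the second vital-signs reading.

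The reading matters because Protocol 4.4 and 7.5.2.3 both warn of infusion-related hypotension, and the synopsis makes clinically significant vital-sign changes a safety endpoint. Adverse event reporting is only a partial backstop: Protocol 9.6.2 discourages reporting vital-sign abnormalities as adverse events, with exceptions, and an asymptomatic change that was never measured cannot be reported at all.

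There is also a small effect on the tables. SAP 2.4.5.3 summarises vital signs by visit without separating pre- from post-infusion values. Under SAP 2.5.2 and 2.5.3, when two readings lie equally far from the target day, the later one is used. Two readings on one day always tie in this way, so the visit value would be post-infusion where that reading was taken and pre-infusion where it was not.

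**Working it through.** No plan figure needs reproducing; the check is a side-by-side reading with counts.

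**Infusion visits.** Table 5 has two (Week 1 Day 1, Week 3 Day 15) and Table 6 has three (Weeks 24, 48, 72): 2 + 3 = 5.

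**Required window (6.3.7), vital signs and ECG alike.** 60 − 15 = 45 to 60 + 15 = 75 minutes after infusion, plus a reading within 2 hours before.

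**What the schedule carries:**

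| Source | Vital signs | ECG |
|---|---|---|
| Tables 5–6, row footnote giving the pre/post window (footnote 9) | 0 of 2 tables | 2 of 2 tables |
| Tables 5–6, row footnote giving pre-infusion timing (footnote 13) | 2 of 2 tables | 0 of 2 tables |
| Appendix F checklist, marked pre and post | 0 of 5 visits | 5 of 5 visits |
| Appendix F sequence list, before infusion | 5 of 5 visits | 5 of 5 visits |
| Appendix F sequence list, after infusion | 0 of 5 visits | 5 of 5 visits |

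**One ambiguous line.** At Week 1 Day 1 the first post-infusion item gives a time but no procedure. Its time is 30 ± 15 minutes. The Labs field of the same visit gives the PK sample as "at 30 minutes +/- 15 minutes after end of infusion on infusion day", so the line matches PK. The PK window is 30 − 15 = 15 to 30 + 15 = 45 minutes; the vital-signs window is 45 to 75 minutes. The two meet only at 45 minutes, so this is not a vital-signs line that lost its label.

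**Footnotes.** The superscripts were read from extracted text and should be confirmed on the page. The Appendix F counts do not depend on them.

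**Consequence in the SAP.** SAP 2.1.4 takes as safety baseline the last value before the first dose, which at Week 1 Day 1 is ordinarily the pre-infusion reading. A subject with no later reading that day contributes a change from baseline of 0, or no change value, to that visit's summary. SAP 2.4.5.5 avoids this mixing for the ECG by tabulating by visit and time point; SAP 2.4.5.3 has no such split for vital signs. Any value that is recorded still enters the any-time incidence, the worst-status shift table and the listing in SAP 2.4.5.3.

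**The case against.** The best case against is that this is an omission and not a contradiction. Footnote 13 does not say that vital signs are taken only before the infusion. It also sits on several other rows (EDSS, questionnaires, MRI, urinalysis, immunoglobulins), where it works as a general instruction to finish these before dosing, and it suits the physical examination that shares the row. A site can comply with the footnote, Appendix F and 6.3.7 together. Appendix F gives no clock time for the post-infusion ECG either, which suggests a summary checklist and not a rival timing rule.

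There are practical safeguards too. Section 7.5.2.3 requires at least an hour of monitoring after the first two infusions. Section 7.5.2.4 requires close monitoring after an interruption for a reaction, with the infusion resumed only when vital signs are normal. Vital signs are taken again on Week 1 Day 2. The infusion log, institutional monitoring (7.5.2.1) and DSMB review of blood pressure all continue, and the eCRF may prompt the reading. Finally, splitting the SAP summaries could be called a matter of presentation.

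Most of this stands as a limit on severity. None of it supplies the missing prompt. The one-hour monitoring is waived at Weeks 24, 48 and 72 unless a reaction has been seen. The ECG keeps the subject on site in the right window, but it does not record blood pressure. A Day 2 reading is not a 60-minute reading. Appendix F does name the ECG after the infusion, timed or not, and does not name vital signs. The SAP split would be useful in any case, and it is what stops uneven collection from mixing two kinds of value in one summary.

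**Conclusion.** The inconsistency is real and should be corrected; it is minor. It extends to all five infusion visits and appears in both parts of the schedule, the tables and Appendix F. Section 6.3.7 is taken as the intended rule because it states the window expressly and pairs it with the ECG.

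The documents do not show how many readings would be lost, since the eCRF and infusion log are not included, and a prompt there could reduce the loss to nothing. The claim is limited to this: a site working from the schedule could omit the reading, some asymptomatic blood-pressure changes might then go unrecorded, and the by-visit summaries could mix pre- and post-infusion values. No efficacy analysis is affected, and there is no ground for expecting bias between arms.

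**What to change.** 1. **Appendix F:** at each of the five infusion visits, add vital signs at 60 ± 15 minutes after the end of infusion to the post-infusion list.
2. **Tables 5 and 6:** attach footnote 9 to vital signs and leave footnote 13 on the physical examination.
3. **SAP 2.4.5.3:** present the by-visit vital-signs summaries by time point (pre- and post-infusion), as SAP 2.4.5.5 does for the ECG.
4. **Optional, Protocol 7.5.2.3:** state that the Week 24, 48 and 72 monitoring waiver does not remove the 60-minute vital signs and ECG.

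The cost is wording only: five lists, one row in each of two tables, one SAP sentence and, if wanted, one further protocol sentence. No procedure is added, because 6.3.7 already requires the reading and the post-infusion ECG already keeps the subject on site in the same 45 to 75 minute window.

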6.4 REPLACEMENT POLICY

Subjects who discontinue and/or withdraw from the study for any reason will not be replaced.

6.5 DEFINITIONS

Evaluable for toxicity. All subjects will be evaluable for toxicity from the time of their first treatment on Week 1 Day 1.

Evaluable for radiological and neurological response. Only those subjects who have had a pre-treatment baseline efficacy evaluation and at least one post-treatment efficacy evaluation will be considered evaluable for response. These subjects will have their response classified according to the definitions stated below.

6.6 DISEASE PARAMETERS

Measurable disease: Diagnosis of RMS will be based on the 2010 McDonald's criteria (Appendix C).

6.7 DURATION OF RESPONSE

Duration of stable disease:

Stable disease is measured from the start of the treatment (Week 1 Day 1) until the criteria for relapse or progression of disease are met or there is evidence of new radiological activity as assessed by MRI, taking as reference the smallest measurements recorded since the treatment started, including the baseline measurements.

6.8 RESPONSE REVIEW

Subjects will be assessed for relapse by the Treating Neurologist at screening, baseline (pre-dose), and all scheduled visits and, if necessary, at unscheduled visits. If a relapse is suspected, the Treating Neurologist and Examining Neurologist will follow the procedures as outlined in Section 6.3.1.

MS relapses are defined as new or worsening neurological symptoms lasting ≥ 24 hours with the absence of fever, injury, infection or adverse reactions to medications. The symptoms are attributed to MS and are preceded by 30 days of stability. The change in EDSS score as assessed by the Examining Neurologist is ≥ 0.5 increase from prior visit or ≥ 2 points increase on one of the appropriate FS or 1 point on two or more of the appropriate FS.

6.9 RE-SCREENING PROCEDURES

Subjects may be re-screened under the following conditions:

- After a relapse recovery (see Section 4.4.1) and upon re-consent
- Varicella titer does not indicate immunity at initial screening and subject is re-immunized (see Section 3.2)
- He/she, at initial screening, is not eligible to participate in the study based on inclusion/exclusion criteria (Sections 3.1 and 3.2) and wishes to re-assess eligibility after a waiting period deemed sufficient by the site investigator.
- The subject was determined eligible, but 28 days or more has elapsed between the initial screen and the first infusion (Week 1 Day 1).

Re-screening procedures are identical to initial screening procedures (Appendix F), but with the following modifications:

- Medical history does not need to be taken again.
- Screening MRI may not need to be repeated if there was one obtained within 30 days prior to this screening

6.10 END OF STUDY FOLLOW-UP

After early termination of trial or at the end of study visit at Week 96, subjects will enter a 20-week Follow-up Period inclusive of the accelerated elimination of teriflunomide. The 11-day elimination procedure will commence at Week 100 for all subjects who completed all study visits including Week 96. For those subjects who had terminated early (discontinued or withdrawn from the study), the 11-day elimination procedure will commence the day after the Early Withdrawal from Treatment Visit. The follow up period will include visits at Weeks 100, 104, and 116. Weeks 108 and 112 will be performed via a phone call.

For subjects who withdraw their consent to participate in the study, the site should inform these subjects of the 20-week Follow-up Period inclusive of the accelerated teriflunomide elimination procedure and document this in the eCRF. Participation in the 20-week Follow-up Period inclusive of the accelerated teriflunomide elimination procedure for subjects who withdraw early is left to the discretion of the subject. If he/she elects not to participate in the 20-week Follow-up inclusive of the accelerated teriflunomide elimination procedure, after withdrawing consent and after discussion with the site, it should be documented in the eCRF.

For subjects who will participate in the 20-week Follow-up Period inclusive of the accelerated teriflunomide elimination procedure after withdrawing consent for this study, a new consent form to participate in the 20-week Follow-up Period inclusive of the accelerated teriflunomide elimination procedure will need to be signed. If he/she re-consents, the sites will complete the eCRF for Weeks 100, 104, 108, 112, and 116, accordingly.

The purpose of this follow-up is to monitor safety and relapses after the discontinuation of study medications and to eliminate residual teriflunomide from the study subjects. Because blinding is maintained until the data from the treatment period (through Week 96) is locked, all subjects will undergo the accelerated teriflunomide elimination procedure regardless of whether they were randomized to ublituximab/oral placebo or teriflunomide/IV placebo. Study subjects that enter the Follow-up Period of TG1101-RMS302 (post-Week 96 to Week 116) are not allowed to receive DMTs. Please refer to the exclusion criteria of the protocol for a list of MS therapies (Section 3.2). It should be noted that use of systemic corticosteroids for the treatment of a relapse is allowed. When deciding

TG1101-RMS302

Dated: 04 September 2020 (Ver. 5.0)

Page 66 of 140

to treat a potential acute relapse the Treating Neurologist can use IVMP (1.0 g/day for at least 3 days and can be extended to 5 days).

The procedures of each visit are below:

Week 100 Visit:

- Physical examination and vital signs
- Urine pregnancy test
- Report concomitant medications and Adverse Events
- Initiate rapid teriflunomide elimination program (Section 6.10.1 below)
- Hematology and serum chemistry, urinalysis, and B cell assays (as per Section 6)

Week 104 Visit:

- Physical examination and vital signs
- Urine pregnancy test
- Report concomitant medications and Adverse Events
- Hematology and serum chemistry, urinalysis, and B cell assays (as per Section 6)
- Acknowledgment of the completion of teriflunomide rapid elimination program by the site on eCRF

Week 108 and 112 (Phone Call):

- Follow-up phone call to subject to collect information on concomitant medications, Adverse Events and urine pregnancy test outcomes

Week 116 Visit (Final Visit):

- Physical examination and vital signs
- Urine pregnancy test
- Report concomitant medications and Adverse Events
- Teriflunomide drug concentration test: Draw blood to test teriflunomide plasma concentration

TG1101-RMS303 is a 172-week open label extension (OLE) trial. Subjects completing 96-weeks of treatment in TG1101-RMS301 or TG1101-RMS302 trials in United States, Croatia, Ukraine, Russia, Republic of Belarus, Serbia, Poland, and Georgia may be eligible to participate. Regardless of which treatment group the subject was assigned to in the core study, all subjects enrolled in the OLE will receive ublituximab on the following schedule: Week 1 Day 1, Week 3 Day 15, and Weeks 24, 48, 72, 96, 120, 144, and 168 or until physician or subject decision to withdraw prior to this time. Subjects will have final assessments done at Week 172. TG1101-RMS302 is considered a core study protocol for OLE. The TG1101-RMS303 subjects, sponsor and investigators will not know TG1101-RMS301 and TG1101-RMS302 treatment assignments until these studies are unblinded.

